Safety endpoints include frequency and severity of adverse events and increased likelihood of developing chronic pain due to TENS treatment. Please see section 13: “Provisions to monitor the data to ensure the safety of subjects,” describes the monitoring of the safety endpoints.

[figure not shown]
9) Procedures Involved*

Overview:

The primary study design will be a randomized, double-blinded, controlled trial of early intervention TENS compared to Sham TENS, with longitudinal tracking of signs and symptoms of NeuP, as well as symptoms and severity of non-neuropathic pains, pain impact, and psychological function, for 12 months post-SCI. **Figure 5** diagrams the study procedures, subject flow, and assessment time points.

Patients will be eligible for recruitment into the study as soon as they have been admitted to the SCI inpatient rehabilitation unit at UM/JMH/Lynn Rehabilitation Center (see Section 21 for full recruitment procedures). Treatment TENS or Sham TENS sessions (see “Randomization procedures,” below) will be initiated within four months post-injury (with four weeks post-injury as the target, if feasible).

Figure 5: Timeline of subject participation and study procedures

* Note the above diagram depicts the anticipated average time course of study procedures across subjects. Due to varying times between injury and admission to/discharge from inpatient SCI rehabilitation, not all subjects will begin participation in the study precisely at the two-month post-injury timepoint.

Subjects will be enrolled and randomized regardless of whether they have NeuP symptoms at initial assessment. Because approximately 25% of SCI patients who report chronic neuropathic pain at 1 year post-injury had initial neuropathic pain symptoms at 1 month post- injury,²¹ initiating treatment at four weeks post-injury will capture approximately 75% of patients before their neuropathic pain symptoms manifest. In those patients who do have neuropathic pain symptoms at the baseline assessment, we will be able to test the ability of TENS to interfere with the transition from acute to chronic neuropathic pain, by comparing the decrease in severity of neuropathic pain symptoms from baseline to 12 months post-injury between the two study groups (Treatment TENS vs Sham TENS).

Once baseline assessments are completed, treatment will be administered twice a week, for 30 minutes each session, for 8 weeks.

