- The Spinal Cord Injury Pain Instrument (SCIPI)⁸⁰ will be used to identify pains that are likely to be neuropathic in nature. This four-item questionnaire has shown sensitivity and specificity of 78% and 73%, respectively, for diagnosing neuropathic pain when using a cutoff score of ≥ 2 on this scale.⁸⁰ The pain classification definitions and guideline presented within the International SCI Pain Basic Data Set 2 (ISCIPIBDS2) will also be used to assist with classification of pain type.

This assessment will be used as the primary outcome measure for Aim 1, indicating the presence or absence of neuropathic pain at each follow-up time point.

ii. Pain intensity and symptoms:

Based on differentiated pains, as reported by the study subject, the intensity of each pain will be rated using a 0 – 10 numerical rating scale (NRS), with 0 being equal to “no pain” and 10 being equivalent to “pain as bad as you can imagine.” Subjects will be asked to “Rate your pain by indicating the number that best describes your pain on average over the past 24 hours,” “over the past week,” and “over the past 3 months.”

This scale, including the phrasing of the anchors and the recall time points, has been suggested as a primary

endpoint for chronic pain clinical trials.⁹² *Changes in pain intensity for neuropathic pains will be calculated across the assessment time points to measure the effectiveness of TENS treatment for those who present with neuropathic pain at baseline [Aim 1], and to assess correlations among pain severity and demographic and psychological factors [Aim 2].*

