- *The Neuropathic Pain Symptom Inventory (NPSI)⁸⁹ will be used to quantify the severity of neuropathic pain-specific characteristics. This questionnaire has been validated and used in a number of patient populations with various neuropathic pain conditions^{89, 95-98} including those with SCI.^{8, 74} A total NPSI score will be calculated as an indication of the severity of neuropathic pain.⁸⁹ This questionnaire should be distinguished from the SCIPi, which is also used for neuropathic pain, but is intended as a dichotomous *diagnostic screening tool* for neuropathic pain in SCI, whereas the NPSI is intended as an ordinal *measure of neuropathic pain severity. For those subjects with neuropathic pain symptoms at entry into the study, the NPSI total score will be used to determine whether a reduction in neuropathic pain severity is present after TENS treatment, and during longitudinal follow-up [Aim 1]. This measure will also be used to examine associations between neuropathic pain severity and demographic and psychosocial factors [Aim 2].**
- We will also capture specific information about the presence and severity of different qualities of the pain experience for each pain location the subject describes using the short-form McGill Pain Questionnaire 2 (SF-MPQ2)⁹⁹ as secondary outcome measures of sensory and affective components of pain. The SF-MPQ2 is a revised version of the SF-MPQ¹⁰⁰ to include both qualities of pain associated with nociceptive pain types and those associated with neuropathic pain types. Desirable psychometric properties of the SF-MPQ2 have been documented in a number of pain patient populations.^{99, 101-103} *Responses to specific pain qualities will assist with pain diagnosis, and total scores and subscale scores of “continuous pain,” “intermittent pain,” “neuropathic pain,” and “affective descriptors” will be used in secondary analyses of TENS effectiveness [Aim 1] and relationships with other outcomes of interest [Aims 2].*

iii. Maladaptive pain coping:

- The Pain Catastrophizing Scale (PCS)¹⁰⁴ measures the degree to which individuals engage in a maladaptive pain coping style that is characterized by exaggerated and ruminating negative cognitions and emotions during painful situations. The PCS has demonstrated high validity and reliability.¹⁰⁵ *Measures obtained from the PCS will be used to prospectively track its potential as a pre-disposing factor for the development of chronic pain after SCI [Aim 2].*
- iv. Sensory function:

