Based on a total sample size of 98 subjects, and an estimated 15% drop-out rate, we expect that approximately 82 subjects will complete the study (i.e., 41 subjects per treatment arm). Based on previous work,^{21, 59} we project that 60% of subjects in the Sham TENS (control) group will have at- or below-level neuropathic pain at the 12 month follow-up time point. Thus, with 41 subjects in each group, $\alpha = 0.05$, power of at least 80%, and an analysis based on a two-sided Z-test (for group difference in proportion of subjects with neuropathic pain) for *Hypothesis 1a*, we will be able to detect at least a 50% reduction in the rate of subjects with chronic neuropathic pain in the TENS treatment group compared to the Sham group at 12 months post-SCI (i.e., Sham TENS = 60% with neuropathic pain; Treatment TENS = 30% neuropathic pain).

For t-test analyses assessing differences between groups (Sham vs. Treatment) using continuous variables (e.g., NRS, NPSI), 41 subjects in each group will allow for detection of a medium-to-large effect size (i.e., Cohen's $d = 0.6$) with α set at 0.05 and power of 0.80. Paired correlations will also be used for additional analyses (*Aim 2*). For correlations within group ($n = 41$), with power set at 0.80 and $\alpha = 0.05$, we will be able to detect a medium-to-large effect size (i.e., Cohen's $f^2 = 0.20$), and we will be able to detect a small-to-medium effect size for across-group analyses ($n = 82$; Cohen's $f^2 = 0.10$).

Data analysis plan:

Descriptive evaluations of the data will be performed for all variables to check the integrity of the data and to verify the underlying assumptions of the statistical tests that are planned. If necessary, and as appropriate, data will be transformed prior to any parametric analyses, or non-parametric techniques will be used with untransformed data. Statistical analyses will use two-tailed tests and an a-priori α of 0.05.

In addition to direct tests of hypotheses (described in detail below), descriptive analyses and graphical representations (e.g., spaghetti plots) of data will be used to describe longitudinal

characteristics of clinical pain, somatosensory function, and other physical and psychological outcomes across the 12-month timeline of study participation.

Hypothesis 1a:

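### The test promised in subjects with neuropathic pain at baseline has no single named scale, no entry in the analysis plan, and low power at any size the documents suggest

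*Combined protocol and SAP*

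**What the plan says.** The statement is in section 9 (Procedures Involved), Overview. Patients are randomized whether or not they have neuropathic pain at entry. For those who do, "we will be able to test the ability of TENS to interfere with the transition from acute to chronic neuropathic pain", by comparing between arms the decrease in severity from baseline to 12 months. That sentence names no instrument.

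The list of assessment tools in section 9, under pain intensity and symptoms, then names two:

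- **NRS:** "Changes in pain intensity for neuropathic pains will be calculated across the assessment time points to measure the effectiveness of TENS treatment" in those who present with neuropathic pain at baseline. The NRS is asked for three recall windows (24 hours, one week, three months), and no window is singled out.
- **NPSI:** in those with symptoms at entry, "the NPSI total score will be used to determine whether a reduction in neuropathic pain severity is present after TENS treatment", and also during later follow-up.

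Both are tagged to Aim 1.

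Section 11 (Data Management) sets a general rule: "Statistical analyses will use two-tailed tests and an a-priori α of 0.05". Its only power statement for continuous scales such as these is that "41 subjects in each group will allow for detection of a medium-to-large effect size", given as d = 0.6 with power 0.80. Under Hypothesis 1a, subjects with early pain appear once, through a separate rule for being counted positive at 12 months (a rating of at least 4 out of 10). The NRS and NPSI comparisons described there are between whole arms. The section gives no severity analysis within the baseline-pain subgroup, no expected subgroup size and no exploratory label. Allocation is in blocks of eight, with no stratification by baseline pain stated.

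**The concern.** The Overview presents this comparison as the trial's answer for patients who already have pain when treatment starts. Two things are missing for it to be that.

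First, the deciding measure is left open. The NRS and the NPSI can disagree, and nothing in the plan says which one settles the question. With each tested at 0.05, the chance that at least one is significant under no effect exceeds 5%.

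Second, the number of subjects is unstated, and the only power figure offered for these scales is for full arms. A non-significant result in a small subgroup says little about whether TENS affects the transition, yet the wording invites the reader to treat the comparison as a test that could settle it.

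**Working it through.** **1. The plan's own figures.** The plan expects "an estimated 15% drop-out rate, we expect that approximately 82 subjects will complete the study (i.e., 41 subjects per treatment arm"). Check: 98 x 0.85 = 83.3, close to the stated 82. For the primary endpoint ("i.e., Sham TENS = 60% with neuropathic pain; Treatment TENS = 30% neuropathic pain"; "power of at least 80%, and an analysis based on a two-sided Z-test"), 41 per arm gives power 79.0% with a pooled variance and 81.7% unpooled, so the stated figure is reproduced to within rounding. For the continuous scales, a two-sided t-test with 41 per arm has noncentrality 0.6 x sqrt(41/2) = 2.72 on 80 degrees of freedom and power 76.5%. The d detectable with 80% power is 0.63, which rounds to the stated 0.6.

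**2. Size of the subgroup.** The documents give no figure, so I derive scenarios per arm among completers.

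- *Near-floor.* The section 9 Overview says about 25% of those with chronic neuropathic pain at one year had symptoms at one month. Section 11 projects 60% with neuropathic pain at 12 months under sham. 0.25 x 0.60 x 41 = 6.2, about 6 per arm. This leaves out early pain that resolves. It also uses a one-month figure, although treatment may start up to four months after injury.
- *The 25% read as a share of all patients.* 0.25 x 41 = 10.3, about 10 per arm.
- *Generous case.* Every projected 12-month case already has pain at baseline: 0.60 x 41 = 24.6, about 25 per arm. This is more than the protocol expects. The electrode-placement text in section 9 says most subjects will have no neuropathic pain at enrolment, which means fewer than 0.5 x 41 = 20.5 per arm.

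**3. Power in the subgroup.** Two-sided t-test at 0.05, noncentrality 0.6 x sqrt(n/2), 2n - 2 degrees of freedom:

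| n per arm | Power at d = 0.6 | d detectable with 80% power | 95% CI half-width (SD units) |
|---|---|---|---|
| 6 | 15% | 1.80 | 1.29 |
| 10 | 25% | 1.32 | 0.94 |
| 20 | 46% | 0.91 | 0.64 |
| 25 | 55% | 0.81 | 0.57 |
| 41 (plan) | 77% | 0.63 | 0.44 |

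**4. Chance of at least one false positive, each test at 0.05.** The correlation between tests is an assumption.

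- *Two tests (NRS and NPSI at 12 months).* Independent: 1 - 0.95^2 = 9.75%. By simulation: 9% at correlation 0.5 and about 8% at 0.7 to 0.8. Range about 8-10%.
- *Four tests (both scales, end of treatment and 12 months).* Independent: 1 - 0.95^4 = 18.5%. By simulation: about 16% at 0.5 and about 11% at 0.8. Range about 11-18%. This case applies only if an end-of-treatment test is run on both scales.

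**5. Comparing decreases versus adjusting for baseline.** With equal SDs at the two visits and baseline-to-12-month correlation r, the variance of a change score is 2(1 - r) SD^2 and the ANCOVA residual variance is (1 - r^2) SD^2. Their ratio is (1 + r)/2: 0.65 at r = 0.3 and 0.85 at r = 0.7. ANCOVA therefore has 35% to 15% lower variance at these assumed correlations.

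Adjustment helps power but does not rescue the claim. If d = 0.6 is in units of the 12-month SD, a strong correlation of 0.66 gives an effective d of 0.6/sqrt(1 - 0.66^2) = 0.80. Power is then 24% at 6 per arm, 40% at 10, 69% at 20 and 79% at 25.

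**The case against.** The strongest reply is that the plan is less open than it looks. The Overview sentence fixes a single time point, 12 months. Section 9 names the NPSI, not the NRS, as an Aim 1 primary outcome variable, and its NPSI paragraph addresses subjects with symptoms at entry. Read together, NPSI change to 12 months is the best-supported contrast, and the real ambiguity is one extra scale. This largely stands. It still requires the reader to make the inference, because section 11 lists NRS and NPSI side by side as secondary outcomes and the NRS paragraph assigns the same task to the NRS.

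A reader might infer that every monthly assessment on both scales will be tested at 0.05, with a far higher error rate. The documents do not support that. The NRS text says changes will be calculated and names no test, and section 11 plans descriptive analyses and plots for the longitudinal course of pain. Only the NPSI wording about the period after treatment leaves room for an end-of-treatment test.

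A reader might also infer that the subgroup result is offered as confirmatory. It is not among Hypotheses 1a to 2c, the section 8 endpoints or the section 11 hypothesis tests, and section 11 names one primary analysis. The Overview sentence is loosely worded prose explaining why symptomatic patients are enrolled. Nor do the documents say that a favourable scale would be picked or that a null result would be read as no effect. Those are risks left open, not stated intentions.

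**Conclusion.** The point holds as a minor one. The protocol says it can test the acute-to-chronic transition in subjects with baseline neuropathic pain, fixes the time point, leaves the scale open between NRS and NPSI, and gives the comparison no place in section 11.

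Under the blanket 0.05, the false-positive chance for the two scales at 12 months is about 8-10%. It reaches about 11-18% only if end-of-treatment tests are added. The number of tests is not stated, and these ranges rest on assumed correlations.

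The power conclusion is firmer, because it does not depend on one assumed size: 15% at the near-floor of about 6 per arm and about 55% at 25 per arm, which exceeds what the protocol itself expects. The documents give no firm upper figure for the subgroup. The d = 0.6 statement for 41 per arm does not apply to it. The primary comparison of proportions is unaffected.

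**What to change.** In section 11, add one analysis for subjects with neuropathic pain at baseline: 12-month NPSI total compared between arms by ANCOVA on baseline NPSI, replacing the comparison of decreases. Label it exploratory, report the estimate with a 95% CI, and state the expected subgroup size. List the NRS and all other time points in this subgroup as descriptive.

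In the section 9 Overview, replace the claim of being able to test with *will explore*. State that the d = 0.6 power figure does not apply to this subgroup.

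An arm-by-baseline-pain interaction in all subjects may be added as supportive only. It is less precise than the subgroup contrast: with equal SDs and a 6/35 split per arm, its standard error is sqrt(1 + 6/35) = 1.08 times as large. In addition, baseline NPSI will be near zero in subjects without baseline pain, so it overlaps with the subgroup indicator.

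The cost is protocol wording and one model on data already collected. The trial gives up a firm test claim in this subgroup, which the design could not support.

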The primary statistical analysis, to test the effectiveness of prophylactic TENS for neuropathic pain after SCI will be via a two-proportion z test, comparing the percentage of subjects in the TENS treatment group who are “positive” for neuropathic pain at 12 months post-injury to the percentage of subjects in the Sham TENS group who are positive for neuropathic pain at 12 months post-injury. Subjects who score a 2 or more on the SCIPPI for a pain located at or below their neurological level of injury at the 12 month follow-up time point will be considered positive for neuropathic pain. Subjects who do not have a pain at- or-below the level of injury or a score of 2 or more on the SCIPPI will be considered negative for neuropathic pain. For those subjects who have neuropathic pain symptoms early after injury (i.e., prior to entering the study), a “positive” result for neuropathic pain will be defined as having neuropathic pain that is moderate or greater (rated at least a 4 out of 10) at the 12 month follow-up assessment.

Additional analyses will be conducted using secondary outcomes collected at the 12-month time point: 1) comparison of pain severity (using the NRS and NPSI scores) between the groups (This analysis will be especially important if the primary analysis does not show a difference in rates of the presence of neuropathic pain at 12 months.); 2) comparison of use of analgesics between groups; and 3) comparison of response to pain interference questions from the ISCPBDS2. General linear model analyses will be used, with TENS group (Treatment vs. Sham) as a categorical predictor of these secondary outcome measures.

Separate analyses for at-level neuropathic pain and below-level neuropathic pain, as well as nociceptive pains, will also be conducted to examine whether TENS differentially impacts their development or severity. Additional analyses will be conducted, using the diagnosis of each pain type according to ISCPBDS guidelines, as determined and agreed upon by our study staff pain experts, as a confirmation of the primary neuropathic pain metric (SCIPPI ≥ 2).

Hypothesis 1b:

To investigate factors that may be related to patient responsiveness to TENS as a preventive treatment for chronic neuropathic pain, we will assess correlations between changes in evoked pain (before and after TENS treatments) and the presence and severity of neuropathic pain

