symptoms at the 12 month post-injury time point. It is anticipated that those who show reduced sensitivity to noxious stimuli after TENS treatments will exhibit a lower risk for chronic neuropathic pain. A repeated measures regression analysis, including appropriate covariates (e.g., demographic and injury-related factors, concomitant treatments, amplitude setting of TENS treatments), will assess whether changes in evoked pain sensitivity will be a significant predictor of neuropathic pain at 12 months post-injury in the TENS treatment group.

Hypotheses 2a, 2b, and 2c:

Chi square analyses, t-tests, and correlations across all subjects (with TENS group assignment as a covariate) will be used to separately examine whether demographic variables (age and minority status), psychological characteristics (pain catastrophizing, depressive symptoms severity, and levels of resilience), and measures of evoked pain sensitivity (pain thresholds and ratings of suprathreshold noxious stimuli) measured at baseline can predict the presence and severity of chronic neuropathic pain at 12 months post-SCI. Separate sub-analyses will also be conducted with regard to the impact of these factors on pains with different diagnostic categories (nociceptive pain, neuropathic pain).

Data security / Quality control:

All research personnel will complete and maintain trainings regarding privacy and data security as required. All personnel will receive training regarding all study procedures as required for their role, as assigned and overseen by the PI, to insure data quality and integrity of the science.

Data for the study will be recorded on paper, using the most-updated and approved study forms. These paper documents will be stored in locked file cabinets in rooms 3.156 and 3.153B of the Christine E. Lynn Rehabilitation Center ([name]). This room is locked and is accessible only by those who have been given card access. These paper documents will be stored for at least 3 years after the final termination of the grant.

Data from the paper documents will be entered into a password protected electronic database that will receive periodic and thorough data quality checks through established procedures. This

electronic file will not contain any personally-identifiable information, and will be maintained for at least 3 years after the final termination of the grant.

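### In subjects with neuropathic pain at baseline, the between-arm comparison of the decrease in severity to 12 months has no baseline adjustment; ANCOVA would be more precise in most settings and would not move with chance imbalance

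*Combined protocol and SAP*

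**What the plan says.** Section 9 (Overview) enrols subjects whether or not they already have neuropathic pain. For those who do, it plans to test whether TENS interferes with the transition from acute to chronic pain "by comparing the decrease in severity of neuropathic pain symptoms from baseline to 12 months post-injury between the two study groups". It names no scale, model or covariate.

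Two entries under Pain intensity and symptoms in section 9 concern the same subjects. For the NRS: "Changes in pain intensity for neuropathic pains will be calculated across the assessment time points to measure the effectiveness of TENS treatment". For the NPSI: "the NPSI total score will be used to determine whether a reduction in neuropathic pain severity is present after TENS treatment", and also during longitudinal follow-up.

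Section 11 does not mention the comparison of decreases. Under Hypothesis 1a it compares 12-month NRS and NPSI scores between arms: "General linear model analyses will be used, with TENS group (Treatment vs. Sham) as a categorical predictor of these secondary outcome measures". Group is the only predictor named. Covariates for outcome models appear only under Hypothesis 1b, within the TENS arm ("A repeated measures regression analysis, including appropriate covariates (e.g., demographic and injury-related factors, concomitant treatments, amplitude setting of TENS treatments"), and for Aim 2, where group is the covariate. Baseline pain severity is in neither place.

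Randomisation is in blocks of eight, four per arm, with no stratification by baseline pain stated.

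**The concern.** The plain reading of the Overview is a comparison of change scores. Baseline falls roughly one to four months after injury, so the two measurements are about 8 to 11 months apart in a changing condition, and their correlation could well be modest. A change score then carries the baseline noise as well as the outcome noise.

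It also over-corrects for a chance difference at baseline. If the slope of 12-month on baseline severity is below 1, the arm that happens to start with more pain shows a larger decrease through regression to the mean alone. In a small subset without stratification, a sizeable chance difference is to be expected.

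At stake are the width of the interval and the stability of the estimate in the one comparison that the protocol ties explicitly to the acute-to-chronic transition.

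**Working it through.** **The plan's own figure.** The nearest stated figure is for continuous outcomes in all completers: "41 subjects in each group will allow for detection of a medium-to-large effect size", given as d = 0.6 at power 0.80 with two-sided alpha 0.05. The detectable effect is (1.960 + 0.842) × √(2/41) = 0.62 (0.63 by the t-test), and power at exactly 0.60 is 0.775 (t-test 0.765). So 0.6 looks like rounding and has no bearing here. No sample size or power is stated for the baseline-pain subset.

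**Subset size (assumed).** Section 9 says about 25% of those with chronic neuropathic pain at one year had symptoms at one month. Section 11 projects 60% with neuropathic pain in the sham arm and about 82 completers.
- 0.25 × 0.60 × 82 ≈ 12, or 6 per arm. This leaves out early pain that resolves.
- 0.25 × 82 ≈ 20, or 10 per arm, if a quarter of all completers have baseline pain.
- The subset is larger if baseline falls later than four weeks.

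**Precision.** Let both SDs equal 1 and the correlation be r.
- Variance of the change score: 2(1-r).
- Residual variance under ANCOVA: 1-r².
- Ratio of ANCOVA to change: (1+r)/2, so the loss is (1-r)/2.

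Estimating the slope multiplies the ANCOVA variance by about 1 + 1/(N-4), where N is the total in the subset: 1.0625 for N = 20 and 1.125 for N = 12. The loss becomes 1 - (1+r)/2 × that factor.

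| r | Loss, slope known | Loss, 10 per arm | Loss, 6 per arm |
|---|---|---|---|
| 0.2 | 40% | 36% | 33% |
| 0.6 | 20% | 15% | 10% |
| 0.8 | 10% | 4% | none (-1%) |

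A simulation with 10 per arm gave losses of 37%, 16% and 5% at these three values.

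**Unequal SDs.** For a 12-month to baseline SD ratio k between 0.75 and 2 and r between 0.2 and 0.8, the loss (slope known) runs from 0% to 57%. It is zero when r × k = 1. At k = 1.25 it is 27% at r = 0.2 and 6% at r = 0.6.

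**Power for a true difference of 0.8 SD** (illustrative; r from 0.2 to 0.6; two-sided 0.05; ANCOVA simulated with its lost degree of freedom):
- 10 per arm: change score 27-47%, ANCOVA 39-54%.
- 6 per arm: change score 17-29%, ANCOVA 23-32%.
- 6 per arm at r = 0.8: change score 51%, ANCOVA 50%.

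**Chance imbalance.** With 10 per arm the baseline difference between arms has an SD of √(2/10) = 0.45 baseline SD. Given an observed imbalance, the change-score contrast shifts by (1 - slope) × imbalance, where slope = r × k, which is r for equal SDs. For a one-SD imbalance at r = 0.3 that is 0.7 × 0.45 = 0.31 SD. In simulation with no true effect:
- Over all randomisations the change score averaged 0.00.
- In trials where the TENS arm started higher, it showed a false benefit of 0.29 SD (r = 0.2), 0.18 SD (r = 0.5) or 0.07 SD (r = 0.8).
- ANCOVA showed 0.00 in those same trials.

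**The case against.** The Overview describes procedures; it is not the analysis plan. It names no model, and a regression of the decrease on arm with baseline as a covariate would also compare decreases, with the same arm estimate as ANCOVA of the 12-month score. This is fair: that the comparison is unadjusted is the plain reading, not an explicit statement. But no adjustment is recorded anywhere and section 11 is silent, so the model needs naming on either reading.

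A reader might infer that the NRS and NPSI entries in section 9 also prescribe a between-arm comparison of unadjusted decreases. They do not. They say that changes will be calculated and that a reduction will be looked for over time, and those longitudinal uses are legitimate.

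A reader might also infer that this is the only evidence planned for subjects with early pain. It is not. Hypothesis 1a gives them their own positivity rule at 12 months (pain of at least 4 out of 10) and compares 12-month NRS and NPSI between arms. Section 8 likewise defines the severity endpoint at 12 months, not as a change.

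Finally, the subset is underpowered under either analysis: at 10 per arm, ANCOVA reaches only about 39-54% for a 0.8 SD difference. This stands. It limits what the fix can deliver but is no reason to prefer the less precise method.

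**Conclusion.** The concern holds for the comparison in the Overview: a between-arm contrast of decreases with no specified baseline adjustment, which ANCOVA improves on in most plausible settings.

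It would be tempting to say that the plan throws away 20-40% of the information. The protocol does not support that as a fact. The range needs r of 0.2-0.6 and equal SDs, and the protocol gives no baseline-to-12-month correlation or SD for the NRS or NPSI; its reliability table covers sensory thresholds only. At the likely subset sizes the range is lower, and at r near 0.8 the advantage is small or absent.

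Nor should a reader conclude that the method biases the trial. The change score is unbiased over all randomisations and keeps the type I error. The shift is conditional on an observed imbalance, and it favours the arm starting with more pain only if the slope is below 1.

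This is a worthwhile correction to a subgroup severity analysis. The primary two-proportion test is untouched.

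**What to change.** In the section 9 Overview, and carried into section 11 under Hypothesis 1a, state that in subjects with neuropathic pain at baseline the between-arm comparison is a linear model of the 12-month score on arm and the subject's own baseline score on the same scale. Fit it for the NPSI total and separately for the NRS. Report the adjusted arm difference with its 95% CI, and show unadjusted change descriptively.

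Keep the longitudinal uses of the NRS and NPSI in section 9, and adjust any between-arm comparison made there for baseline in the same way.

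The cost is wording only. Table 2 already schedules both scales at the baseline and 12-month full assessments, so no extra subjects, visits or measurements are needed. Fixing the model in advance also removes a later choice between the change score, the 12-month score and the adjusted score, which can disagree in a subset this small.
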